6.4 Study Time Intervals

Monthly Interval for Efficacy Endpoints

Monthly efficacy measurements will be calculated based on the subject's monthly IP dosing schedule defined below using eDiary data collected from beginning of the baseline phase (week -4 visit) up to week 76 (end of eDiary use). Any eDiary data occurring after EOS date will not be included in the analysis.

Study Phase	Assessment Timepoint	Start Date	End Date
Baseline Phase	Baseline	LogPad assignment date (Week -4 study visit)	Day prior to study day 1
Double-blind Treatment Phase	Week 4	
• Study Day 1	
• Week 4 dose date-1• Study day 28 if Week 4 dose is not received (either missed or IP discontinued prior to Week 4)
	Week 8	
• Week 4 dose date• Study day 29 if Week 4 dose is not received (either missed or IP discontinued prior to Week 4)	
• Week 8 dose date-1• Study day 56 if Week 8 dose is not received (either missed or IP discontinued prior to Week 8)
	Week 12	
• Week 8 dose date	
• Week 12 IP dose date-1• Study day 84 if Week 12

		
• Study day 57 if Week 8 dose is not received (either missed or IP discontinued prior to Week 8)	dose is not received (either missed or IP discontinued prior to Week 12)
	Week 16	
• Week 12 dose date• Study day 85 if Week 12 dose is not received (either missed or IP discontinued prior to Week 12)	
• Week 16 dose date-1• Study day 112 if Week 16 dose is not received (either missed or IP discontinued prior to Week 16)
	Week 20	
• Week 16 dose date• Study day 113 if Week 16 dose is not received (either missed or IP discontinued prior to Week 16)	
• Week 20 IP dose date-1• Study day 140 if Week 20 dose is not received (either missed or IP discontinued prior to Week 20)
	Week 24	
• Week 20 dose date• Study day 141 if Week 20 dose is not received (either missed or IP discontinued prior to Week 20)	
• Week 24 IP dose date-1• Study day 168 if Week 24 dose is not received (either missed or IP discontinued prior to Week 24)
Open-label Treatment Phase	Week 28	
• The 1st OL dose day	
• Week 28 dose date-1• OLTP day 28 if Week 28 dose is not received (either missed or IP discontinued prior to Week 28)

	Week 32 or later when eDiary is used	
• Same rule as above	
--	--------------------------------------	--	--

Study Visit

Since the actual visit for a subject may not exactly coincide with their targeted visit date, the actual visit date is mapped to the study visit as follows.

Study Visit	Target Day	Study Day
Baseline		Please refer to Section 6.3 Baseline Assessment of the Study
Day 1	1	1
Week 4	29	16-43
Week 8	57	44-71
Week 12	85	72-99
Week 16	113	100-127
Week 20	141	128-155
Week 24	169	
• 156 to (week 24 OLTP dose date – 1) for subjects who receive OLTP dose at week 24• 156-183 for subjects who did not receive OLTP dose at week 24
Week 28	197	
• Week 24 OLTP dose date to 211 for subjects who receive OLTP dose at week 24• 184-211 for subjects who received at least one OLTP dose and did not

		receive OLTP dose at week 24 (e.g., first OLTP dose was postponed)
Week 32	225	212-239
Week 36 to Week 72	Following same monthly windowing as Week 32	
Safety follow-up	Based on visit name from RAVE or other source data	

Note:

If more than one visit (including the unscheduled visits, ie, CPEVENT = 'UNSCHED') fall within the same defined window, scheduled visit will be used regardless of the distance from the target day. Unscheduled visit will only be used when there is no scheduled visit in the defined window. The closest visit to the target day among the same type of visit (scheduled vs. unscheduled) will be considered for analysis. If two assessment dates are equidistant from the target date, the latter visit will be considered for analysis.

For safety analyses which are summarized by study phase, analysis windows will be set up based on study phase:

Study Phase	Start Time Point	End Time Point
Double-Blind Treatment Phase	Study Day 1 after the 1 st DB IP Dose	
First OL Dose Date for subjects who receive OL IP dose;Min(EOS Date, last IP dose date + 112 days) for subjects who do not receive any OL IP dose
Open-Label Treatment Phase	1 st OL IP Dose Date	Min(EOS Date, last OL IP dose date + 112 days)
Entire Study	Study Day 1 after the 1 st DB IP Dose	Min(EOS Date, last IP dose date + 112 days)

Note: all antibody data will be included in antibody analysis.

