1.3 Exploratory

- To evaluate the effect of AMG 334 compared to placebo on change from baseline in headache impact scores as measured by the Headache Impact Test (HIT-6)
- To evaluate the month of onset of action of AMG 334 compared to placebo as assessed by monthly migraine days
- To evaluate the effect of AMG 334 compared to placebo on the change from baseline in mean monthly migraine attacks
- To evaluate the effect of AMG 334 compared to placebo on change from baseline in mean monthly headache (migraine and non-migraine headache) days
- To evaluate the effect of AMG 334 compared to placebo on the proportion of subjects with at least 75% reduction from baseline in mean monthly migraine days
- To evaluate the effect of AMG 334 compared to placebo on the proportion of subjects with 100% reduction from baseline in mean monthly migraine days
- To evaluate the effect of AMG 334 compared to placebo on change from baseline in monthly acute headache medication treatment days
- To evaluate the effect of AMG 334 compared to placebo on change from baseline in monthly hours of migraine headache
- To evaluate the effect of AMG 334 compared to placebo on change from baseline in monthly average severity of migraine pain
- To evaluate the effect of AMG 334 compared to placebo on change from baseline in mean monthly migraine days with severe pain
- To evaluate the effect of AMG 334 compared to placebo on change from baseline in mean monthly hours of severe migraine pain
- To evaluate the effect of AMG 334 compared to placebo on migraine pain interference with daily activities as measured by the migraine symptom interference items

- To evaluate the effect of AMG 334 compared to placebo on the change from baseline in the overall impact on everyday activities score as measured by the Migraine Physical Function stand-alone item
- To evaluate AMG 334 pharmacokinetics (PK) in subjects with migraine and characterize the exposure-response (E-R) relationships for efficacy and safety endpoints
- To investigate the dose-response relationship of AMG 334 for efficacy
- CCI [REDACTED]
- CCI [REDACTED]
- To evaluate the long-term safety, tolerability and maintenance of effect of AMG 334 after 100 weeks of treatment

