3. EXPERIMENTAL PLAN

3.1 Study Design

This is a Phase 2, multicenter, randomized, stratified, double-blind, placebo-controlled, parallel-group study of subjects with episodic migraine. The study is composed of an initial screening phase (up to 3 weeks), a 4-week baseline phase, a 24-week double-blind treatment phase, a 76-week OLTP, and a 12-week safety follow-up phase (16 weeks after the last dose of investigational product).

Approximately 459 eligible subjects will be randomized 2:1:2:2 to:

- Placebo (n ≈ 131)
- AMG 334 28 mg (n ≈ 66)
- AMG 334 70 mg (n ≈ 131)
- AMG 334 140 mg (n ≈ 131)

The randomization will be stratified by prior/current treatment with migraine prophylactic medication (current migraine prophylactic medication treatment vs prior migraine prophylactic medication treatment only vs no prior or current migraine prophylactic medication treatment).

Investigational product (ie, placebo or AMG 334) will be dosed QM, SC.

The overall study design is described by a [study schema](#) at the end of the Protocol Synopsis Section.

The study endpoints are defined in [Section 10.1.1](#).

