7.2.13 Clinical Outcomes Assessments (COAs) and Electronic Diaries (eDiaries)

Clinical Outcome Assessments (COAs) will be collected by subjects using a handheld eDiary at various frequencies.

The eDiary will collect the following COAs daily, at home:

- Date and time of start of headache (ie, migraine or non-migraine headache)
- Date and time of end of headache
- Worst pain severity per headache
- Pain features (eg, one-sided, throbbing, worsens with exercise/physical activity)
- Symptoms (eg, aura, nausea, vomiting, photophobia, phonophobia)
- Use of acute headache medications (medication name [from pre-entered list], date of dosing, number of times taken on each date)

The eDiary will collect the following patient-reported outcomes (PROs):

- Migraine symptom interference items, daily, at home
- Migraine Physical Function Impact stand-alone item, daily, at home
- Headache Impact Test (HIT-6), monthly, in clinic

Site study staff will assign and provide an eDiary to the subject at the week -4 visit (after confirming the subject's eligibility to enter the baseline phase). The site study staff will train the subject on how to use the eDiary (eg, turning on/off, charging, navigating screens, transmitting data, contacting the help desk for technical assistance) and complete the questions. The subject will be instructed to interact with the eDiary every day during the baseline phase and between the day 1 and week 52 study visits, between the week 72 and week 76 study visits, **between the week 96 and week 100/ET study visits**, and to bring the eDiary to every study visit during these periods. At the day 1 study visit the investigator will use the subject's eDiary to review all data entered during the baseline phase and confirm the relevant inclusion and exclusion criteria. **During these periods the subject will bring the eDiary to every study visit.**

Please refer to the eDiary manual for additional details.

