2.3 Exploratory

- To evaluate the effect of AMG 334 compared to placebo on change from baseline in headache impact scores as measured by the Headache Impact Test (HIT-6)
- To evaluate the month of onset of action of AMG 334 compared to placebo as assessed by monthly migraine days
- To evaluate the effect of AMG 334 compared to placebo on the change from baseline in mean monthly migraine attacks
- To evaluate the effect of AMG 334 compared to placebo on change from baseline in mean monthly headache (migraine and non-migraine headache) days

- To evaluate the effect of AMG 334 compared to placebo on the proportion of subjects with at least 75% reduction from baseline in mean monthly migraine days
- To evaluate the effect of AMG 334 compared to placebo on the proportion of subjects with 100% reduction from baseline in mean monthly migraine days
- To evaluate the effect of AMG 334 compared to placebo on change from baseline in monthly acute headache medication treatment days
- To evaluate the effect of AMG 334 compared to placebo on change from baseline in monthly hours of migraine headache
- To evaluate the effect of AMG 334 compared to placebo on change from baseline in monthly average severity of migraine pain
- To evaluate the effect of AMG 334 compared to placebo on change from baseline in mean monthly migraine days with severe pain
- To evaluate the effect of AMG 334 compared to placebo on change from baseline in mean monthly hours of severe migraine pain
- To evaluate the effect of AMG 334 compared to placebo on migraine pain interference with daily activities as measured by the migraine symptom interference items
- To evaluate the effect of AMG 334 compared to placebo on the change from baseline in the overall impact on everyday activities score as measured by the Migraine Physical Function stand-alone item
- To evaluate AMG 334 pharmacokinetics (PK) in subjects with migraine and characterize the exposure-response (E-R) relationships for efficacy and safety endpoints
- To investigate the dose-response relationship of AMG 334 for efficacy
- CCI [REDACTED]
- [REDACTED]
- [REDACTED]
- To evaluate the long-term safety, tolerability and maintenance of effect of AMG 334 after 76 weeks of treatment

3. Study Overview

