6.5 Subject Disposition

Randomized

Individuals are considered randomized if they have been assigned a randomization number. Randomized individuals are referred to as “subjects”.

Completing the Double-Blind Treatment Phase

Subjects are defined as completing the DBTP if they complete week 24 assessment. It will be derived from the End of Double-Blind Treatment Phase CRF page with “Completed” as the reason for ending study phase.

Completing the Open-Label Treatment Phase

Subjects are defined as completing the OLTP if they complete the week 76 assessment. It will be derived from the End of Open-Label Treatment Phase CRF page with “Completed” as the reason for ending study phase.

Completing Study

Subjects are defined as completing study if they complete the whole 88 weeks of study evaluation. It will be derived from the End of Study CRF page with “Completed” as the primary reason for ending study.

Exposed to Investigational Product

Subjects are defined as exposed if they receive at least one dose of investigational product.

Completing the Double-Blind Investigational Product

Subjects are defined as completing double-blind investigational product if they complete week 20 IP dose or temporarily withhold IP at week 20 and continue to receive IP during OLTP. It will be derived from the End of IP DBTP CRF page with “Completed” as the reason for ending IP.

Completing the Open-Label Investigational Product

Subjects are defined as completing open-label investigational product if they complete week 72 IP dose. It will be derived from the End of IP OLTP CRF page with “Completed” as the reason for ending IP.

On-study

Subjects are considered on-study if they have been randomized and have not yet had their end of study visit.

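### SAP 6.4 was not aligned with Amendment 2: the Week 96–100 diary month is cut off and the visits from Week 76 to Week 100 have no analysis window

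*SAP*

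**What the plan says.** **SAP.** Section 1 ties the plan to Protocol 1.0 of June 2015 and states that it covers both the primary and the final analysis. Its long-term objective (2.3) is "maintenance of effect of AMG 334 after 76 weeks of treatment", and Section 3.1 describes a 52-week open-label phase. Section 6.4 derives monthly efficacy measurements "using eDiary data collected from beginning of the baseline phase (week -4 visit) up to week 76 (end of eDiary use"). Its visit-window table ends with the row "Week 36 to Week 72", apart from safety follow-up. On disposition, Section 6.5 states: "Subjects are defined as completing open-label investigational product if they complete week 72 IP dose". The same section places open-label completion at the Week 76 assessment and study completion at 88 weeks. Open-label efficacy and PRO summaries are tabulated by visit (10.5.3, 10.5.4). ANC, ALT and AST changes are also by visit (10.6.2), and vital signs are summarised over time (10.6.3). Section 11 records no changes from the protocol.

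**Protocol (Amendment 2, June 2017).** Section 3.1 has "a 76-week OLTP, and a 12-week safety follow-up phase (16 weeks after the last dose of investigational product"). Dosing continues through Week 96 and monthly visits through Week 100 (Table 3 and its footnotes). The diary is used again "between the week 96 and week 100/ET study visits" (7.2.13). The objective in Section 1.3 is "maintenance of effect of AMG 334 after 100 weeks of treatment". The synopsis places the final analysis after follow-up to Week 112, and Section 10.5.1 leaves methodological detail to the SAP.

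**The concern.** The SAP is the document from which the final analysis would be programmed, and its calendar stops 24 weeks before the protocol's open-label phase does. A by-visit table needs a rule that assigns each observation to a visit. For diary data the stated rule ends at Week 76. For clinic visits there is no rule after Week 72.

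At stake is the efficacy half of the 100-week objective. The Week 96–100 diary month is the only diary evidence on whether the effect persists to 100 weeks, and the SAP's stated limit leaves it out. Amendment 2 also raised the open-label dose in some subjects so that a continuous year of safety data would be available (Protocol 2.3). A subject in the OL70-140 sequence may spend up to 24 open-label weeks on 70 mg and so change dose as late as Week 24 + 24 = 48. A year at the new dose then ends at Week 48 + 52 = 100, but the by-visit windows end at Week 72, only 24 weeks after the change.

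If the gap is left open, the late rules will have to be written once open-label results are already known.

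**Working it through.** **1. Reproduce both timelines.**
- SAP: 24 + 52 + 12 = Week 88. Last dose plus follow-up gives 72 + 16 = 88. This matches SAP 6.5.
- Protocol: 24 + 76 + 12 = Week 112. Last dose plus follow-up gives 96 + 16 = 112. With screening and baseline, 3 + 4 + 24 + 76 + 12 = 119 weeks, as in Protocol 3.6.1.

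Each document is consistent with itself. They describe different designs.

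**2. Reproduce the SAP's visit windows.** For visit week w, target day = 7w + 1 and window = target − 13 to target + 14.
- Week 4: target 29, days 16–43. Week 8: 57, days 44–71. Week 12: 85, days 72–99. Week 32: 225, days 212–239. All agree with the SAP table.
- Week 72, the last one defined: target 505, days 492–519.

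**3. Count the visits without a window.** Monthly open-label visits after Week 24, from Week 28 to Week 100: (100 − 28)/4 + 1 = 19. Those after Week 72 are Weeks 76, 80, 84, 88, 92, 96 and 100, so 7 of 19 (37%). Under the SAP's own 52-week phase there are 13 such visits (Weeks 28 to 76). Week 76 is still without a window, although SAP 6.5 uses the Week 76 assessment to define open-label completion.

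**4. Size the diary loss.** Nominal open-label diary days under Protocol 7.2.13:
- Weeks 24–52: 28 × 7 = 196
- Weeks 72–76: 28
- Weeks 96–100: 28
- Total: 252

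Only the last block lies beyond the SAP limit: 28/252 = 11.1%. The protocol collects no diary data between Weeks 76 and 96, so none can be lost there.

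**5. Check what is not affected.** The SAP's phase-based safety window for the open-label phase ends at the earlier of end of study and last open-label dose + 112 days. A Week 96 dose falls nominally on day 7 × 96 + 1 = 673, and 673 + 112 = 785, the Week 112 target day (7 × 112 + 1). Adverse events in Weeks 76–100 are therefore inside the window. The open-label exposure formula (6.6) has no week limit, and 6.4 takes all antibody data.

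**6. Extend the rule.** Continuing the 28-day pattern gives Week 76 = days 520–547, Week 80 = 548–575, Week 84 = 576–603, Week 88 = 604–631, Week 92 = 632–659, Week 96 = 660–687 and Week 100 = 688–715. The added diary interval is nominally days 673–700.

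**The case against.** The strongest reply is that this is version lag and not a decision to drop data. The SAP states that it serves Protocol 1.0, and its objective, phase lengths and cut-offs all agree with that design. The Week 76 limit can be read as describing when diary use ended at that time, because the only express exclusion in the same paragraph is of diary data after end of study. The last row of the interval table is open-ended: it covers Week 32 and any later point at which the diary is in use. Protocol 10.4.4 says that the final analysis takes in all periods and all data. The objective is exploratory, and the open-label summaries are descriptive with no formal testing.

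Much of this stands. Version lag is the cause, but it does not cure the gap, because the same SAP governs the final analysis and reports no departures from the protocol. The open-ended row makes the diary rule ambiguous at best, since the sentence that governs the table names Week 76. Nothing comparable rescues the visit windows, and the missing Week 76 window does not depend on the amendment.

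Three stronger readings are tempting, and the documents do not support them:
- *The safety part of the 100-week objective cannot be addressed.* Phase-level safety summaries are not capped by week. Only by-visit safety tables are affected.
- *About a third of the open-label data is lost, as 24/76 = 32%.* That is calendar time. The diary loss is one interval of 28 days, and the phase-level safety data from the seven visits are kept.
- *A subject who stops after the Week 72 dose would be counted as a completer.* The text definition reads that way, but SAP 6.5 derives completion from the CRF reason field. Misclassification would need that field to say completed.

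**Conclusion.** The point holds for by-visit data and for the late diary month. As written, the SAP excludes the Week 96–100 diary interval and gives no window to the seven visits from Week 76 to Week 100. HIT-6, vital signs and the ANC/ALT/AST changes therefore have no defined place in by-visit tables wherever they are scheduled at those visits. The maintenance-of-effect part of the 100-week objective cannot be analysed from the SAP text.

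The diary loss is small in quantity, about 11% of nominal open-label diary days, but it is the one interval that bears on 100 weeks. The Week 24 primary analysis, its sample size and the phase-level safety summaries are untouched.

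The conclusion assumes that the SAP reviewed here is the version that will govern the final analysis, and that its visit-window table is applied literally. The 11% uses nominal visit days for a subject who completes every diary period.

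**What to change.** Amend the SAP before the final analysis:
- Cite Amendment 2 in Section 1, describe the 76-week open-label phase in Section 3.1, and change objective 2.3 to 100 weeks.
- In Section 6.4, move the diary limit to Week 100 and add a Week 96–100 interval. No dose is given at Week 100, so the interval's end should be stated explicitly: nominally study day 700, which is open-label day 700 − 169 + 1 = 532. The Week 72–76 interval already lies within the present limit.
- Extend the visit windows from Week 76 (days 520–547) to Week 100 (days 688–715) under the existing 28-day rule.
- In Section 6.5, align the text definitions with the protocol's last dose at Week 96, final open-label visit at Week 100 and follow-up to Week 112, and check that they agree with the CRF reason fields.

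The cost is one SAP amendment and a small programming change. No new data collection is needed, and the primary analysis does not change.

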10.6.2 Laboratory Test Results

Shifts tables of the laboratory toxicity for absolute neutrophil count (ANC) based on CTCAE grade relative to baseline will be tabulated by treatment group for each study phase.

Summary of change from baseline for ANC, alanine transaminase (ALT) and aspartate aminotransferase (AST) will also be provided by visit for each study phase.

Subject incidence of liver function test abnormalities (including AST, ALT, Total Bilirubin (TBL) and Alkaline Phosphatase (ALP)) will also be summarized by treatment group and study phase.

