10.6.3 Vital Signs

The analyses of vital signs (systolic/diastolic blood pressure and weight) will include summary statistics of change from baseline over time by treatment group.

Systolic blood pressure and diastolic blood pressure may be analyzed by change from baseline in categories: 10-20 mmHg and \geq 20 mmHg and analyzed for SBP >140 mmHg (Yes vs. No) and DBP > 90 mmHg (Yes vs. No) at each time point.

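### SAP 6.4: for subjects dosed open-label at Week 24, the pre-dose Week 24 clinic visit falls in the Week 28 window and never maps to Week 24

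*SAP*

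**What the plan says.** In SAP 6.4, "the actual visit date is mapped to the study visit as follows". For subjects given their first open-label dose at Week 24, the Week 24 row is "156 to (week 24 OLTP dose date – 1) for subjects who receive OLTP dose at week 24" and the Week 28 row is "Week 24 OLTP dose date to 211 for subjects who receive OLTP dose at week 24". Subjects not dosed that day keep the ordinary Week 24 window, days 156 to 183. When several visits share a window, scheduled visits take precedence over unscheduled ones, and "The closest visit to the target day among the same type of visit (scheduled vs. unscheduled) will be considered for analysis".

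A second table in SAP 6.4 covers phases: "For safety analyses which are summarized by study phase, analysis windows will be set up based on study phase". There the double-blind phase ends on the "First OL Dose Date for subjects who receive OL IP dose", and the open-label phase starts on that same date.

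Three kinds of output depend on these tables or may do so:
- **Laboratory (SAP 10.6.2):** "Summary of change from baseline for ANC, alanine transaminase (ALT) and aspartate aminotransferase (AST) will also be provided by visit for each study phase".
- **Vital signs (SAP 10.6.3):** the analyses "will include summary statistics of change from baseline over time by treatment group", with no mention of phase. Protocol 10.5.5 requires all safety analyses separately by phase.
- **HIT-6:** SAP 6.6 lists it among the endpoints computed on the monthly diary intervals. SAP 9.3 and Protocol 7.2.13 treat it as a clinic-visit measure.

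Protocol section 7 puts all procedures for a visit on one day. Protocol 7.2.24 and footnote 15 to the schedule of assessments allow the first open-label dose only after all Week 24 procedures are complete.

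**The concern.** For a continuing subject, the Week 24 assessment date is the open-label dose date. The table gives that date to Week 28, although everything measured at the visit came before the dose. With dosing on target day 169, the Week 24 window is 156 to 168 and excludes its own target. Weeks 4 to 20 are also dosing visits, yet their windows keep the dosing day. Ending an interval the day before the dose suits a diary interval, but not a clinic visit held on the dose day.

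Week 24 closes the double-blind phase. In Protocol Table 2 it is the last of three post-baseline double-blind chemistry and hematology visits (Weeks 4, 12 and 24) and the only one after Week 12. If continuing subjects leave that row, those who remain are a selected group. It includes subjects who stopped double-blind product early, because Protocol 7.2.24 bars them from the open-label phase.

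**Working it through.** **Inputs.** Target days and windows come from the SAP 6.4 Study Visit table. Visit tolerances come from Protocol section 7: ±3 days in the double-blind phase and ±4 in the open-label phase. The rule that dose date equals visit date comes from Protocol sections 7 and 7.2.24.

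1. *Reproduce the table.* Target = 7 × week + 1, and standard window = target − 13 to target + 14. This matches every row from Week 4 to Week 32. For Week 24: 7 × 24 + 1 = 169, window 156 to 183. For Week 28: 7 × 28 + 1 = 197, window 184 to 211.

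2. *Permitted days.* Week 24: 169 ± 3 = 166 to 172 (7 days). Week 28: 197 ± 4 = 193 to 201 (9 days). Combinations: 7 × 9 = 63.

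3. *Apply the rule for dosed subjects.* With dose and visit on day D, the Week 24 window is [156, D − 1] and the Week 28 window is [D, 211]. Day D is never in the first and always in the second, so 0 of 7 permitted days map to Week 24.

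4. *What happens to the record next.* The Week 24 visit lies 197 − 172 = 25 to 197 − 166 = 31 days from the Week 28 target. The true Week 28 visit lies at most 4 days away.
   - Visits selected before any phase split: the Week 24 record is discarded in 63 of 63 combinations.
   - Records split by phase first: the double-blind data stop at D, so the true Week 28 visit cannot compete. The Week 24 record is kept and labelled Week 28 in 63 of 63.
   - Week 28 visit missing: the Week 24 record stands as Week 28 under either order.

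5. *HIT-6 under the diary intervals (SAP 6.6).* The month-6 interval runs from the Week 20 dose date to the day before the Week 24 dose. The clinic score inside it is the one taken at Week 20. Likewise the Week 12 and Week 16 scores fill months 4 and 5.

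6. *Phase table.* Day D satisfies both the double-blind end and the open-label start, so the pre-dose record qualifies for both phases.

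7. *Illustrative count (assumed share).* 0.80 × 459 = 367, leaving 92; 0.95 × 459 = 436, leaving 23. In a 131-subject arm, 131 × 0.20 = 26 and 131 × 0.05 = 7 remain. In the 28 mg arm, 66 × 0.20 = 13 and 66 × 0.05 = 3 remain. These are upper limits, since some of those subjects will have no Week 24 visit.

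8. *After correction.* With windows [156, D] and [D + 1, 211], 7 of 7 Week 24 days map to Week 24, and both visits are correctly placed in 63 of 63 combinations.

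**The case against.** The window boundary itself is hard to dispute. The SAP 6.3 assumption that same-day measurements precede dosing is stated for baseline only, and visit name is used only for safety follow-up. The objections concern the consequences, and several of them stand.

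- *HIT-6.* A reader might infer that the month-6 value is simply lost. The documents do not support that as a flat statement. It requires the Study Visit table to govern HIT-6, whereas SAP 6.6 points to the diary intervals. It requires no phase split, whereas SAP 10.5.4 models patient-reported outcomes within the double-blind phase. It also requires a Week 28 visit to exist, and late enrollees may not have one when the primary analysis is run. What survives is that neither routing uses the true Week 24 score as month 6.
- *Laboratory values.* A reader might infer that they are always mislabelled. That holds if the phase split comes first; otherwise they are discarded. The SAP does not state the order, but the Week 24 row is wrong either way.
- *Phase-level safety summaries.* A reader might infer that they are wholly untouched. The double-blind summaries do keep the record, but the shared boundary date lets it into the open-label ones as well.
- *Intent and detection.* SAP 10.1 plans a pre-open-label baseline for efficacy endpoints, which suggests that Week 24 values were meant to be pre-open-label. A nearly empty Week 24 row might also be noticed during output verification. The Appendix B code is redacted, so the programming cannot be checked. This lowers the practical risk but does not correct the written rule.
- *Stakes.* Safety tables carry no between-group testing (SAP 10.6), HIT-6 is exploratory, and nothing is lost from the database. This limits the severity.

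**Conclusion.** The rule is wrong as written; severity is low to moderate. For every subject dosed open-label at a protocol-compliant Week 24 visit, the pre-dose visit cannot map to Week 24. The double-blind Week 24 row for ANC, ALT and AST then holds essentially only subjects not dosed that day. Vital signs, and the PK concentrations by visit in SAP 10.5.5, are affected in the same way if they use this table.

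For HIT-6, the Week 24 score is labelled Week 28 or dropped under the Study Visit table; under the diary intervals the Week 20 score takes its place. Continuing subjects still contribute through the other months, and SAP 10.5.4 plans no sensitivity analysis for patient-reported outcomes that would show the problem.

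A reader might infer that the primary result is at risk. It is not: the primary and both secondary efficacy endpoints use the diary intervals, where stopping the day before the dose is appropriate. Antibody data are exempt from the windows.

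The conclusion rests on dosing and assessment falling on the same day, as the protocol requires. The share dosed that day is not in the documents, so the counts of 367 to 436 are illustrative only.

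**What to change.** 1. In the Study Visit table, for subjects dosed open-label at Week 24, make the Week 24 row run from day 156 to the Week 24 OLTP dose date inclusive, with same-day scheduled assessments taken as pre-dose. Start the Week 28 row on the Week 24 OLTP dose date + 1 and end it on day 211.
2. In the phase table, assign scheduled assessments on the first open-label dose date to the double-blind phase only. Leave the phase assignment of adverse events as it is.
3. State in SAP 6.6 that HIT-6 uses the Study Visit table, not the monthly diary intervals.

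The cost is two table cells and two sentences, with no new data. The drawback is that an assessment actually taken after the dose that day would count as pre-dose, which the protocol's procedure order makes unlikely.
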